17.3. OTHER EFFICACY VARIABLES

17.3.1. OTHER EFFICACY VARIABLES & DERIVATIONS

Tumor response and its components (target lesion response, non-target lesion response, timepoint response, and best overall response) were not clearly stated as analysis endpoints in the protocol; however, these measurements support the planned analysis endpoints and the protocol specified some supportive summaries and analyses which are described in this section.

Briefly, a disease assessment based on CT scan and/or MRI is planned every 8 weeks (± 7 days), counting from C1D1. Tumor response is determined using RECIST v 1.1 and recorded in the Disease Assessment eCRF. Best overall response is collected once per subject, on the Subject Status - Completion eCRF. A best response of CR or PR must be confirmed no less than 28 days after the criteria for response are first met.

Tumor response and best overall response are determined independently by the investigator and the central radiology reviewers. The central radiology review consists of assessment by 2 independent reviewers, followed by adjudication of the results if the 2 reviewers disagree. The primary and all secondary efficacy endpoints are based on these tumor response assessments plus any recorded subject death.

[Note: Clinical symptoms of disease progression are recorded as adverse events. Bone imaging scans and brain scans provide additional documentation of disease.]

17.3.2. MISSING DATA METHODS FOR OTHER EFFICACY VARIABLES

No imputation of missing data will be performed for tumor response or best overall response.

17.3.3. ANALYSES OF OTHER EFFICACY VARIABLES

Tumor response (investigator and consensus of the blinded central radiology reviewers) will be summarized by treatment group and visit. The number of subjects who were assessed at each visit will be reported. The number and percentage of subjects who had each possible response will be tabulated for the target lesions, the non-target lesions, and the (timepoint) overall response.

Best overall response (investigator and consensus of the blinded central radiology reviewers) will be tabulated for each treatment group using the crude proportion of subjects whose best response during the course of protocol treatment is Complete Response (CR), Partial Response (PR), Stable Disease (SD), Progressive Disease (PD) and non-evaluable (NE). Subjects with a rating of NE will be included in the denominator.

Swimmer lane plots will be produced for FAS subjects, showing duration of treatment, start of complete response, start of partial response, response episode end, continuing response (if applicable), and durable responders.

A waterfall plot showing the maximum reduction of sum of diameters of target lesions and the best overall response will be produced for the FAS.

18. QUALITY OF LIFE ANALYSIS

Quality of life is assessed using the ECOG Performance Status (ECOG PS) at Screening, at the end of each Cycle (e.g., approximately every 3 weeks) for the AGS-16C3F subjects, and at each planned visit for the axitinib subjects.

The ECOG-PS will be summarized by treatment group with a shift table from baseline to each subject's worst post-baseline value and from baseline to final assessment in the study. The analyses will be performed in the FAS and PPS.

19. SAFETY OUTCOMES

All analyses and outputs for safety outcomes will be based on the Safety Analysis Set (SAF). There will be no statistical comparisons between the treatment groups for safety data, unless otherwise specified within the relevant section.

19.1. ADVERSE EVENTS

Treatment emergent adverse events (TEAEs) are defined as AEs that started or worsened in severity after the first dose of study drug and until 28 days post the last administration of the study drug or the subject's Safety Follow-Up visit, whichever occurred later. Events that begin on Day 1 will be counted as treatment-emergent.

AEs will be coded to system organ class (SOC) and preferred term (PT) using the Medical Dictionary for Regulatory Activities (MedDRA) Version 18.1 central coding dictionary and will be graded according to the National Cancer Institute (NCI) Common Toxicity Criteria for Adverse Events (CTCAE), version 4.03.

All summaries of AEs will include only treatment-emergent events unless otherwise stated.

Safety will be evaluated based on the incidence of AEs (including Grade 3 and Grade 4 AEs, treatment-related adverse events, serious adverse events, and AEs requiring discontinuation of study treatment). The number and percentage of AEs, SAEs, AEs leading to discontinuation of study treatment, and AEs related to study drug will be summarized by SOC, PT and treatment group. The number and percentage of AEs by severity will also be summarized. Listings of AEs, SAEs, deaths, and events leading to discontinuation of study treatment will be presented.

See Appendix 2 for handling of partial dates for AEs. In the case where it is not possible to define an AE as treatment emergent or not, the AE will be classified by the worst case; i.e. treatment emergent.

An overall summary of the number and percentage of subjects who had events in each of the categories described below will be produced by treatment group and for combined treatment groups.

- Subjects with at least one AE
- Subjects with at least one possibly drug-related AE
- Subjects with at least one AE of CTCAE Grade 3 or Grade 4
- Subjects with at least one possibly drug-related AE of CTCAE Grade 3 or Grade 4
- Subjects with at least one serious AE
- Subjects with at least one possibly drug-related serious AE
- Subjects whose treatment had to be modified due to an AE
- Subjects whose treatment had to be modified due to a possibly drug-related AE
- Subjects who discontinued treatment with study drug because of an AE
- Subjects who discontinued treatment with study drug because of a possibly drug-related AE
- Subjects with at least one AE resulting in death

- Subjects with at least one possibly drug-related AE resulting in death

Listings will include TEAEs and Non-TEAEs. Any AE that was reported with a start date on or after the initiation of non-protocol anticancer treatment will be flagged in the listings.

19.1.1. ALL TEAEs

Incidence of TEAEs will be presented by treatment group, System Organ Class (SOC), and Preferred Term (PT), and will also be broken down further by maximum severity and relationship to study drug. In these tables, SOCs will be presented alphabetically, and PTs will be presented by decreasing frequency of all events in a PT in the AGS-16C3F arm within SOC.

The number and percentage of subjects who reported TEAEs, possibly treatment-related TEAEs, and TEAEs of CTCAE Grade ≥ 3 will also be summarized by treatment group and presented by PT in the order of descending incidence in the AGS-16C3F group.

19.1.1.1. Severity

Severity will be assigned by the investigator according to the CTCAE severity grades. The severity of each event will be recorded as Grade 1 (mild), Grade 2 (moderate), Grade 3 (severe), Grade 4 (life-threatening) or Grade 5 (fatal).

For any interim tables, TEAEs starting after the first dose of study drug with a missing severity will be left missing in the summary tables and identified in the data issues log(s). If the severity of a TEAE is still missing at the time of database lock, the event severity will be left missing and footnoted on the severity table. If a subject reports a TEAE more than once within that SOC/PT, the AE with the worst case severity will be used in the corresponding severity summaries.

19.1.1.2. Relationship to Study Drug

Relationship, as indicated by the Investigator, is collected in response to the question, "Is there a reasonable possibility that the event may have been caused by the study drug? (Yes, No)". A response of "Yes" to this question indicates a related TEAE; a response of "No" indicates an unrelated TEAE.

TEAEs with a missing relationship to study drug will be tabulated as missing. If a subject reports the same AE more than once within that SOC/PT, the AE with the strongest relationship to study drug will be used in the corresponding relationship summaries.

19.1.2. TEAEs LEADING TO DISCONTINUATION OF STUDY DRUG

TEAEs leading to permanent discontinuation of study drug will be identified by using the "Action Taken" field on the Adverse Event eCRF, based on selection of the text value "study drug discontinued".

A summary of the incidence of TEAEs leading to discontinuation of study drug by SOC and PT will be prepared. A listing of TEAEs that led to discontinuation of study drug will be provided.

19.1.3. SERIOUS ADVERSE EVENTS

Serious adverse events (SAEs) are those events recorded as "Serious" on the Adverse Events page of the eCRF. A summary of serious TEAEs by SOC and PT will be prepared. A listing of SAEs will be provided.

19.1.4. GRADE 3/GRADE 4 TEAEs

A summary of Grade 3 and Grade 4 TEAEs by treatment group, SOC, PT, and toxicity grade will be provided. Grade 3 and Grade 4 events will also be listed. [Note: In some places, labels will say “Grade 3 or Grade 4”, depending on the particular usage.]

19.1.5. ADVERSE EVENTS LEADING TO DEATH

TEAEs leading to Death are those events which are recorded on the Serious Adverse Events page of the eCRF as having an outcome of death. A summary of TEAEs leading to death by SOC and PT will be prepared. A listing of AEs that led to death will be provided, based on data from the SAE eCRF.

19.1.6. ADVERSE EVENTS OF SPECIAL INTEREST

Ocular adverse events and diagnoses which are entered as AEs will be reported on the general tables of AEs. A listing of eye-related TEAEs will be provided.

Ocular toxicities based on ophthalmology exams will be reported on the Eye Exam eCRFs and will be graded using the study specific ocular criteria. These will be tabulated separately from the general AE tables. See Section 19.7.1 and Section 19.7.2 for planned analysis and reporting.

19.1.7. CTCAE GRADING OF ADVERSE EVENTS

AEs will be graded using the Common Terminology Criteria for Adverse Events as defined in the CTCAE 4.03 (14 June 2010) grading system. The complete reference document may be found here:

http://evs.nci.nih.gov/ftp1/CTCAE/CTCAE_4.03_2010-06-14_QuickReference_5x7.pdf

Appropriate details will be included in the programming specifications documents.

19.2. DEATHS

Adverse events that led to death are addressed in Section 19.1.5.

This study also collects mortality information on the Survival Follow-Up form, which does not collect a cause of death. All deaths due to any cause during the study will be part of the overall survival analyses (Section 17.2).

19.3. LABORATORY EVALUATIONS

Local laboratories will be used in this study. Results from blood chemistry, hematology, coagulation, urine tests (including parameters calculated from a 24-hour urine collection), and thyroid tests are expected.

No lab data imputation will be performed. Incomplete data may be excluded from some analyses. In cases where an analysis depends on identifying a clinically significant abnormal value, only values which are non-missing and which can be clearly identified programmatically as significantly abnormal will be counted.

19.3.1. LABORATORY PARAMETERS

A list of laboratory assessments to be included in the outputs is included below.

19.3.1.1. Hematology

- Red blood cells
- Hematocrit
- Hemoglobin
- Platelets
- White blood cells
- Absolute neutrophils
- Absolute eosinophils
- Absolute basophils
- Absolute lymphocytes
- Absolute monocytes

19.3.1.2. Serum Chemistry

- Sodium
- Potassium
- Chloride
- Bicarbonate
- Glucose
- BUN
- Creatinine
- Total protein
- Albumin
- Total Bilirubin
- Direct bilirubin
- ALT (SGPT)
- AST (SGOT)
- Alkaline phosphatase
- LDH
- Uric acid
- Calcium
- Magnesium

-
- Phosphorus (Phosphate)
 - C-reactive protein (CRP)

19.3.1.3. Urine Tests

- Urine protein to creatinine ratio (uPCR)

19.3.1.4. 24-Hour Urine Collection

- Urine collection time
- Urine collection volume
- Urine rate of production in ml/hour (derived)
- 24-hour protein

19.3.1.5. Coagulation

- Prothrombin (PT)
- Activated partial thromboplastin time (aPTT)
- International normalized ratio (INR)

19.3.1.6. Thyroid Function Tests

- TSH
- Free T4

19.3.2. LABORATORY SPECIFIC DERIVATIONS

- Unit conversions for laboratory data will be provided in the programming specifications documents.

19.3.3. LABORATORY REFERENCE RANGES AND MARKEDLY ABNORMAL CRITERIA

Quantitative laboratory measurements will be compared with the relevant laboratory reference ranges in SI units and categorized as:

- Low: Below the lower limit of the laboratory reference range
- Normal: Within the laboratory reference range (upper and lower limit included)
- High: Above the upper limit of the laboratory reference range
- Laboratory values that do not have a reference range will not be categorized.

19.3.4. CTCAE GRADING FOR LABORATORY DATA

Laboratory values for 18 analytes (23 CTCAE terms) will be graded by computer, using the Common Terminology Criteria for Adverse Events (CTCAE) grading system v4.03 (14 June 2010). Table J provides details.

Table J. CTCAE Criteria for Evaluation of Laboratory Values

EDC Collection Analyte	CTCAE Term	
	High	Low
Albumin		Hypoalbuminemia
Alkaline Phosphatase	Alkaline phosphatase increased	
ALT (SGPT)	Alanine aminotransferase increased	
AST (SGOT)	Aspartate aminotransferase increased	
Bilirubin, Total	Blood bilirubin increased	
Calcium	Hypercalcemia	Hypocalcemia
Creatinine	Creatinine increased	
Glucose	Hyperglycemia	Hypoglycemia
Magnesium	Hypermagnesemia	Hypomagnesemia
Phosphorus		Hypophosphatemia
Potassium	Hyperkalemia	Hypokalemia
Sodium	Hyponatremia	Hyponatremia
aPTT	Activated partial thromboplastin time prolonged	
WBC		White blood cell decreased
HGB	Hemoglobin increased	Anemia
PLT		Platelet count decreased
Absolute Neutrophils		Neutrophil count decreased
Absolute Lymphocytes	Lymphocyte count increased	Lymphocyte count decreased

The complete reference document may be found here:

http://evs.nci.nih.gov/ftp1/CTCAE/CTCAE_4.03_2010-06-14_QuickReference_5x7.pdf

It is expected that incomplete data will result in a missing CTCAE Grade.

19.3.5. LABORATORY ANALYSIS METHODS

Presentations will use SI Units. Quantitative laboratory measurements reported as “<X”, i.e. below the lower limit of quantification (BLQ), or “>X”, i.e. above the upper limit of quantification (ULQ), will be converted to X for the purpose of quantitative summaries, but will be presented as recorded, i.e. as “<X” or “>X” in data listings.

The following summaries by treatment arm will be provided for laboratory data:

- Incidence of Grade 3 and Grade 4 toxicities, based on the CTCAE grading system, at each subject's worst post-baseline value, safety follow-up assessment, and final assessment
- Shift tables from baseline toxicity grade to worst post-baseline toxicity grade, based on the CTCAE grading system

Listings of all laboratory data collected during the study will be produced. Any positive pregnancy tests will be listed separately.

19.4. ECG EVALUATIONS

19.4.1. ECG ASSESSMENTS

Subjects will have an ECG at screening, on C1D1, and at the end of study safety follow-up visit. Subjects who are randomized to AGS-16C3F will have an ECG at predose and at 2 hours post-dose on C1D1; subjects randomized to receive axitinib will have an ECG at predose only, on C1D1.

ECGs are done in triplicate for all timepoints, approximately 3-5 minutes between each assessment. Each set of results will be identified by a unique recorded clock time. The triplicate values may be considered individually or represented by their median, depending on the analysis. Retests and unscheduled assessments will be included, unless otherwise specified.

The following ECG parameters will be reported for this study:

- HR (bpm)
- PR Interval (msec)
- QRS Interval (msec)
- QT Interval (msec)
- QTcF Interval (msec) [derived]
- Overall assessment of ECG (Investigator's judgment):
 - o Normal
 - o Abnormal, Not Clinically Significant (ANCS)
 - o Abnormal, Clinically Significant (ACS)

Any ECG-related adverse events that are determined by the investigator or medical reviewer to have occurred will be collected on the Adverse Event CRF and reported in the AE tables, listings, and figures.

19.4.2. ECG SPECIFIC DERIVATIONS

- Fridericia's Correction (msec)
 - o $QTcF \text{ (msec)} = \frac{QT \text{ (ms)}}{\sqrt[3]{RR \text{ (ms)}/1000}}$
- RR Interval – If RR Interval is not available for the derivation of the QTc corrections, it will be derived from HR as

o
$$RR \text{ (msec)} = 1000 * \frac{60}{HR \text{ (bpm)}}$$

All components for these calculations must be taken from the same assessment, which will be identified in the database by the date-time of the ECG recording.

19.4.3. CTCAE GRADING OF QT INTERVAL

The Common Terminology Criteria for Adverse Events (CTCAE) grading system v4.03 (14 June 2010) will be used to grade possible ECG QT corrected interval prolongation. The complete reference document may be found here:

http://evs.nci.nih.gov/ftp1/CTCAE/CTCAE_4.03_2010-06-14_QuickReference_5x7.pdf

The initial computerized grading will be based on the QTcF numeric values only, excluding any clinical component. The initial computerized grades will be assigned as shown in Table K and reported on the ECG results listing:

Table K. Criteria for Evaluation of ECG QT corrected interval prolongation

CTCAE Term	CTCAE Grade	One or more of the following conditions:
QTcF prolongation	1	The median of the triplicate measurements at a planned timepoint is within (450 ms ≤ QTcF ≤ 480 ms)
	2	The median of the triplicate measurements at a planned timepoint is within (481 ms ≤ QTcF ≤ 500 ms)
	3	Any 2 of the triplicate measurements are in (501 ≤ QTcF)
	4	The median of the triplicate measurements is within (501 ≤ QTcF) or the median change from baseline among the triplicate measurements is (QTcF change from baseline >60 ms).

[Note: If only 1 measurement is available, the single measurement will be taken as the “median”.]

Grade 3 and Grade 4 values do not automatically qualify as adverse events; there is also a clinical component to determining whether an AE has occurred. For example, a subject who has a median QTcF ≥ 501ms or a median change from baseline >60 ms will be flagged as having a (possible) Grade 4 event according to the computerized criteria. However, the final determination of a Grade 4 event depends on clinical considerations (e.g., occurrence of Torsade de pointes or polymorphic ventricular tachycardia or signs/symptoms of serious arrhythmia).

Therefore, the investigator and/or other medical reviewer will consider the subject’s complete data before making a final determination about recording an ECG-related AE and assigning the final CTCAE grade. The investigator has the final responsibility to record and grade any AE that may have occurred.

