19.4.4. ECG ANALYSIS METHODS

The ECG quantitative data will be summarized by incidence of treatment-emergent Grade 3 or Grade 4 QTcF values by treatment arm. Grade 3 and Grade 4 values will be identified prior to averaging the triplicate ECG results.

Subjects who met the abnormal criterion specified in Section 19.4.3 will be identified on the ECG data listing.

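### SAP Table K makes computerized QTcF Grade 3 and Grade 4 the same condition for a triplicate, and its >60 ms route gives Grade 4 to readings that are all below 501 ms

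*SAP*

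**What the plan says.** SAP 19.4.3 grades QTcF by program, from the numbers alone. In Table K:

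- Grades 1 and 2 are bands on the triplicate median: 450 to 480 ms and 481 to 500 ms.
- Grade 3 applies when "Any 2 of the triplicate measurements are in" the range from 501 ms upward.
- Grade 4 applies when "The median of the triplicate measurements is within (501 ≤ QTcF) or the median change from baseline among the triplicate measurements is" above 60 ms.

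A note covers incomplete sets: "If only 1 measurement is available, the single measurement will be taken as the" median. No rule says which grade prevails when a set meets more than one.

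On use of the grades, 19.4.3 says: "The initial computerized grades will be assigned as shown in Table K and reported on the ECG results listing". Below the table it repeats that either Grade 4 condition alone is enough, calls the result a possible Grade 4, and leaves the final AE grade to the investigator: "However, the final determination of a Grade 4 event depends on clinical considerations".

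Section 19.4.4 then plans the tabulation: "The ECG quantitative data will be summarized by incidence of treatment-emergent Grade 3 or Grade 4 QTcF values by treatment arm". It adds: "Grade 3 and Grade 4 values will be identified prior to averaging the triplicate ECG results". Section 19.4.1 describes the basis differently: "The triplicate values may be considered individually or represented by their median, depending on the analysis".

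**The concern.** A grading table should put each set of readings into one grade, and a higher grade should mean something worse. Table K appears to do neither at the top of the scale. Its Grade 3 row and the first half of its Grade 4 row look like two descriptions of the same finding. The second half of the Grade 4 row asks for no minimum QTcF.

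If so, the listing would show numeric prolongation as Grade 4 although the same section says Grade 4 rests on clinical findings. The by-arm summary of Grade 3/4 values would mix two different things: a QTcF of 501 ms or more, and a rise above 60 ms at any level. This matters because it is the only quantitative ECG summary that 19.4.4 specifies.

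**Working it through.** **Inputs.** The Table K thresholds and the single-reading note (SAP 19.4.3), three readings per time point (19.4.1), and the baseline definition (6.3). The plan gives no figure to reproduce, so the check is logical and the rules were applied literally.

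**Step 1: complete triplicate.** Order the readings a ≤ b ≤ c. The median is b. At least two readings are ≥501 ms if and only if b ≥ 501 ms. The Grade 3 condition and the first Grade 4 condition are therefore identical.

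- 505/510/490: two readings ≥501, median 505. Both conditions met.
- 520/470/475: one reading ≥501, median 475. Neither met (Grade 1 band).

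Enumeration of 40 values from 380 to 560 ms gives 40³ = 64,000 ordered triplicates, with 0 disagreements between the two conditions. Crossed with ten baselines from 370 to 460 ms, 180,320 combinations meet Grade 3. All 180,320 also meet Grade 4, and none is Grade 3 alone.

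**Step 2: incomplete sets.** A lone 505 ms is its own median, so it is Grade 4; it cannot be Grade 3, which needs two readings. A pair of 490 and 520 has median (490 + 520)/2 = 505, so it is Grade 4 only. Grade 3 alone is thus impossible with one, two or three readings. It becomes possible only in a larger set, such as 490/490/501/501 (median 495.5). Section 19.4.1 includes retests, but nothing in the SAP pools them into a triplicate, and 6.5 generally takes the latest retest.

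**Step 3: change above 60 ms.**

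| Baseline (ms) | Post-dose median (ms) | Change (ms) | Band of the median | Table K result |
|---|---|---|---|---|
| 380 | 445 | 65 | below Grade 1 floor | Grade 4 |
| 400 | 466 (465/466/467) | 66 | Grade 1 | Grades 1 and 4 |
| 439 | 500 (all three) | 61 | Grade 2 | Grades 2 and 4 |

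For a 61 ms rise in whole milliseconds:

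- Baselines up to 388 end below 450 (388 + 61 = 449).
- Baselines 389 to 419 end at 450 to 480.
- Baselines 420 to 439 end at 481 to 500.

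On the same grid, 36,356 of 323,776 Grade 4 combinations have all three readings below 501 ms. These counts show that the case exists; they are not expected rates.

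**Step 4: effect on the summary.** For a triplicate, Grade 3 or Grade 4 reduces to median ≥501 ms, or median change >60 ms. The overlap in Step 1 drops out of this union. Only the change condition adds subjects below 501 ms.

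**Step 5: baseline for the change.** Section 6.3 takes the last non-missing measurement. Section 6.5 refers ECG handling to 19.4, which does not say whether baseline is the last reading or the triplicate median. With predose readings 400, 398, 380 and then 445 three times, the change is 445 − 380 = 65 (flagged) or 445 − 398 = 47 (not flagged).

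**The case against.** The best defence is that Table K is a deliberately sensitive screen and says so. The grading is numeric, initial and labelled possible; Grade 3 and 4 values are not automatically AEs; the investigator has the last word. The change condition appears in both the table and the text, so it is no slip. This stands as far as the AE tables go. It does not reach the listing or the 19.4.4 summary, which use the computerized result under a grade label.

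Four stronger inferences are not supported:

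- *Every median of 501 ms or more is listed as Grade 4 and not Grade 3.* That needs a highest-grade rule, and Table K has none. Without one, such a triplicate carries both grades.
- *The overlap inflates the Grade 3/4 count.* If the two grades are pooled, it changes nothing. Whether they are pooled or split depends on output templates that are not among the documents.
- *The reference to averaging in 19.4.4 means each reading is graded separately.* Table K's Grade 3 row already works on individual readings within a set, and 19.4.1 allows individual or median use. The phrase is loose and needs tidying, but it is hardly a second grading rule.
- *The fix should demand two high readings even in incomplete sets.* That would drop a lone 520 ms and the 490/520 pair, both of which the SAP now flags.

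**Conclusion.** The concern holds in limited form. For a complete triplicate, Table K cannot separate computerized Grade 3 from Grade 4: every qualifying set meets both, and Grade 3 is empty if the highest grade is taken. The change condition assigns Grade 4 at any QTcF level, including below 450 ms, and lets the 19.4.4 summary count subjects with no reading at 501 ms or more. This is a rule that gives the wrong result when followed as written, not a missing detail.

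The consequence is small. It touches the ECG listing and one descriptive safety table. Investigator-graded AE tables are unaffected, and SAP 19 plans no statistical comparison of safety data unless a section specifies one; 19.4 specifies none. The number of subjects involved cannot be derived, because neither document gives a QTcF distribution.

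The conclusion assumes that the summary uses the Table K grades, as 19.4.3 and 19.4.4 read together imply, and that retests are not pooled into a triplicate. It is judged against the SAP's own text, since the CTCAE v4.03 wording is cited but not reproduced. It should be corrected, but it is not critical to the trial's conclusions.

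**What to change.** 1. Use one numeric category for 501 ms or more, labelled computerized Grade 3: median of the available readings ≥501 ms. For a triplicate this equals two or more readings ≥501 ms. Keep the note that a single available reading serves as the median.
2. Assign no computerized Grade 4. Take Grade 4 from the investigator's determination, as 19.4.3 already provides.
3. Report median change from baseline >60 ms as its own category, apart from the grades, in both the listing and the 19.4.4 summary. State baseline as the median of the last predose triplicate.
4. In 19.4.4, replace the sentence on averaging with wording that matches these rules.

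Under these rules, 505/510/490, a lone 505 and the pair 490/520 are all computerized Grade 3, so no set of up to three readings now flagged for QTcF of 501 ms or more loses its flag. A rise from 380 to 445 ms has no grade but appears in the change category.

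The cost is SAP wording and minor programming. It needs no new ECGs or data and leaves clinical management unchanged.
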